Mal de Debarquement Syndrome (MdDS) is an under-recognized balance disorder, which in most cases occurs after exposure to prolonged passive motion (a cruise). MdDS is manifested by constant postural rocking and/or swaying and the body's gravitational pull. It is accompanied by high sensitivity to light, noise, crowds, cognitive dysfunctions (thinking challenges), including short-term memory loss. In addition to motion-triggered (MT) MdDS, similar symptoms also occur without a clear trigger, identified as spontaneous MdDS. Recently, we developed an effective treatment method for MdDS based on the readaptation of the vestibulo-ocular reflex (VOR). The hypothesis underlying this treatment is that MdDS is caused by maladaptation of a functional component of the VOR called velocity storage, whose readaptation can be stimulated by exposure to whole-field visual motion. Our current success rate immediately after treatment of MT MdDS is 75%. However, some patients report symptoms returns after flights or prolonged car rides following a treatment. Thus, for some patients, the effectiveness of the current MdDS treatment appears to depend on a serious practical limitation of needing to permanently avoid transportation. Building on the previous hypothesis of velocity storage maladaptation, we currently hypothesize that reduction (habituation) of velocity storage can also resolve MdDS symptoms. Velocity storage can be significantly habituated by 4-5 days of treatment with a protocol previously designed in our laboratory to reduce susceptibility to motion sickness. Preliminary data support that velocity storage habituation reduces MdDS symptoms. In this project, 30 MT MdDS patients with no history of inner ear problems and no severe neurological decoders will be randomly assigned into two groups. Group 1 will be treated with the habituation protocol only, and Group 2 will be treated with the VOR readaptation protocol only. Patients will be followed up for up to 6 months. Based on the preliminary data, we expect both groups to experience similar initial symptom improvement, but the group undergoing the habituation protocol will potentially retain the initial treatment impact. This project hopes to broaden treatment options for MdDS and increase the current understanding of recurrent MdDS.

Background

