Mal de Debarquement Syndrome (MdDS) is an under-recognized balance disorder, which in most cases occurs after exposure to prolonged passive motion. MdDS is manifested by constant postural rocking and/or swaying and by the gravitational pull of the body. It is accompanied by high sensitivity to light, noise, crowds, cognitive dysfunctions, including short-term memory loss. Recently, we developed an effective treatment method for MdDS based on the readaptation of the vestibulo-ocular reflex (VOR). The hypothesis underlying this treatment is that MdDS is caused by maladaptation of a functional component of the VOR called velocity storage, whose readaptation can be stimulated by exposure to whole-field visual motion. Our current success rate immediately after treatment of MT MdDS is 75%. However, some patients report symptoms returns after flights or prolonged car rides following a treatment. Thus, for some patients, the effectiveness of the current MdDS treatment protocol appears to depend on a serious practical limitation of needing to permanently avoid transportation. Building on the previous hypothesis of velocity storage maladaptation, we currently hypothesize that reduction (habituation) of velocity storage can also resolve MdDS symptoms. Velocity storage can be significantly habituated by 4-5 days of treatment with a protocol previously designed in our laboratory to reduce susceptibility to motion sickness.

Specific Aims

The goal of this project is to establish a new effective treatment protocol for Mal de Debarquement Syndrome (MdDS), which not only reduces patients' symptoms but also works in the long term by reducing their susceptibility to recurrent MdDS due to re-exposure to passive motion. This new protocol is expected to liberate treated patients from the possible need to permanently steer away from traveling.

The previously established MdDS treatment protocol is via readaptation of the vestibulo-ocular reflex (VOR), in particular a functional component of the VOR known as velocity storage. Building on the hypothesis of velocity storage maladaptation as the neural basis of MdDS, we currently hypothesize that velocity storage habituation can also resolve MdDS symptoms by minimizing the contribution of the maladapted component of the VOR. The effectiveness of MdDS treatment by the habituation and readaptation protocols will be compared through two Specific Aims.

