Specific Aim 1: Assess the efficacy of MdDS treatment via habituation of velocity storage. It was previously demonstrated that the contribution of velocity storage to the VOR could be eliminated by a habituation protocol. Fifteen MT MdDS patients with no peripheral vestibular abnormalities (Group 1) will undergo this protocol over the period of four days. Objective and subjective symptoms will be assessed with a standardized test battery (**Methods 1**) before and after habituation.

Specific Aim 2: Further assess the efficacy of MdDS treatment via VOR readaptation and compare success rate with Group 1, which underwent the habituation protocol. Fifteen MT MdDS patients with no peripheral vestibular abnormalities (Group 2) will undergo the VOR readaptation protocol over the period of four days. Objective and subjective symptoms will be assessed with a standardized test battery before and after readaptation. Treatment effectiveness will be compared between the two groups immediately and 6 months after treatment.

Number of subjects

| Page

Subjects To Be Enrolled	60
-------------------------	----

Study Timelines

We planning to recruit all 60 patients by August 2022.

Duration Anticipated to Enroll All Study Subjects

18 months

Estimated Date for the Investigators to complete this study

Within 3-5 years

Setting of the Human Research

How Participants Will Be Identified

Vestibular Testing Center at Mount Sinai has treated 3-7 patients with MdDS on a weekly basis, receiving 3-15 applications for treatment per week. The treatment is advertised on web sites of Mount Sinai and Vestibular Testing Center (www.mdds.nyc). We anticipate reaching out to all previously treated MdDS patients who are part of the Vestibular Testing Center's clinical database to offer the study. The study treatment provider ([name], PI) will mail or email the letter discusses the study and the ability for the participant to 'opt out' of being contacted concerning the study.

How Research Will Be Introduced to Participants

Potential subjects will be interviewed over the telephone for confirmation and clarification of their MdDS symptoms. Once the participant potentially meets the entry criteria, they will be consented over the phone following the HRP 093 policy are scheduled for a screening visit or a screening telephone call.

How Participants Will Be Screened

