Randomly selected MdDS patient volunteers will be treated with the velocity storage habituation protocol (Group 1, Aim 1). Another group of randomly selected patients of Group 2 will be treated with readaptation of VOR. Before and after the treatment, the severity of the objective and subjective symptoms will be assessed. Indices of postural stability (Method 1) and time constant of velocity storage (Method 2) will be obtained as objective measures. Treatment will take place over four days. The severity of subjective symptoms will be assessed by a self-reported scale of 0-10, where 0 is no symptom, and 10 is the most difficult sensation of that symptom that the patient can imagine. Among these symptoms are brain fog, head pressure, the fullness of the ear, heavy head, headache, nausea, blurry vision, fatigue, sensitivity to fluorescent lights, scrolling of computer screen, sensitivity to noise, walking on a trampoline, the sensation of

| Page

gravitational pull-up or down. The visual disturbance will be determined by the Visual Vertigo Analogue Scale and Situational Vertigo Questionnaire. Physical, emotional, and functional aspects of disability related to MdDS will be obtained by Dizziness Handicap Inventory (DHI). The patient will undergo follow-up testing for objective and subjective symptoms at 2 weeks, 1 month, 3 months, and 6 months after the treatment.

Treatment will be considered effective if objective and subjective symptoms are improved at least 50%. The effectiveness of the two treatments would be compared immediately after treatment and up to one year of follow-up phone calls.

Description of Procedures Being Performed

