Expected Direct Benefit to Subjects

Symptoms on MdDS could be relieved or significantly reduced.

Benefit to Society

While MdDS is a rare disease, readaptation of the vestibulo-ocular reflex is the only effective method of treatment (75% success rate). In this study, we will test a new method of MdDS treatment and potentially increase the effectiveness of the existing method.

Provisions to Protect the Privacy Interests of Subjects

A unique identification number will be assigned to each enrolled subject. The identification log will be stored separately. All collected digital data (posture, eye movements) will be stored in the directories with the subject's ID. All forms and scoresheets have only subject ID and no identifiable information. All study activities are conducted in a private exam room. All telephone conversations or email will be done in a manner agreed upon by the participant prior to starting the study.

Economic Impact on Subjects

Subjects will have all study activities covered by the research. No payment is being offered for participation

Results of the Study

In this study, we compare the effectiveness of a new method of MdDS treatment to a previously developed method in our lab called the readaptation treatment. Results will be published and presented in peer reviewed journals and conferences. These publications will be shared with participants by email if they wish further information. Also, any participant who wants to receive the same or alternative treatment after completing the follow up can do so clinically.

| Page

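### The end of follow-up is 6 months in some places and one year in another, so further treatment allowed after follow-up may overlap the late comparison

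*Protocol*

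**What the plan says.** Four places in the protocol bear on when follow-up ends.

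- **Opening summary:** "Patients will be followed up for up to 6 months".
- **Specific Aim 2:** "Treatment effectiveness will be compared between the two groups immediately and 6 months after treatment".
- **Description of the Study Design, test schedule:** "The patient will undergo follow-up testing for objective and subjective symptoms at 2 weeks, 1 month, 3 months, and 6 months after the treatment".
- **Description of the Study Design, next paragraph:** "The effectiveness of the two treatments would be compared immediately after treatment and up to one year of follow-up phone calls".

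Results of the Study then makes access to more treatment depend on that end point: "any participant who wants to receive the same or alternative treatment after completing the follow up can do so clinically". That sentence gives no date.

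The summary also says where a difference is expected. Initial improvement should be similar in the two groups, but "the group undergoing the habituation protocol will potentially retain the initial treatment impact".

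**The concern.** The permission for further treatment depends on an end of follow-up that the protocol fixes in two ways. Staff working from the summary, the test schedule and Aim 2 could reasonably treat follow-up as complete at 6 months. The comparison of assigned treatments would then continue for another 6 months while patients are free to receive the same treatment again or the other group's.

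Uptake would probably not be random. Patients who are well have little reason to seek more treatment, and those whose symptoms persist or return have every reason. If the hypothesis is right, Group 2 (readaptation) has more such patients at 6 months. A Group 2 patient who then improves after habituation, and is scored in the assigned group without distinction, counts as a late success of readaptation. A true durability advantage could then look as if it fades between 6 and 12 months.

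Durability is the stated goal of the project, and the one-year calls are the longest evidence on it that the protocol plans.

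**Working it through.** **Step 1. The two readings of the end of follow-up.**

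| Follow-up is complete at | Basis in the protocol | Further treatment opens | 6-month comparison (Aim 2) | 6-to-12-month comparison |
|---|---|---|---|---|
| 6 months | Summary; test schedule; Aim 2 | After the 6-month test | Unaffected | Overlaps with further treatment |
| Last one-year call | Study Design, which calls these contacts follow-up calls | After the last comparison | Unaffected | Unaffected |

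Nothing in the protocol selects one row over the other.

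**Step 2. Size of the dilution under the first reading.** The protocol gives no long-term success rates, no uptake of further treatment and no figure of its own to reproduce. What follows is an illustration.

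Inputs:
- Success at 6 months, p: 70% with habituation and 40% with readaptation (assumed).
- Share of failures retreated, u: 25%, 50% or 75%, equal in both groups (assumed).
- Success of retreatment, s: 75% or 40%. The upper value borrows the readaptation rate from Objectives, "Our current success rate immediately after treatment of MT MdDS is 75"%. That is an immediate rate and not a lasting one. The lower value equals the assumed 6-month rate for readaptation.
- Patients who are successes at 6 months remain so (assumed).

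Formula: success at one year = p + (1 − p) × u × s. The difference between groups is therefore multiplied by (1 − u × s).

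With u = 0.50 and s = 0.75:
- Habituation: 0.70 + 0.30 × 0.375 = 0.8125
- Readaptation: 0.40 + 0.60 × 0.375 = 0.625
- Difference: 18.75 points instead of 30

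With u = 0.50 and s = 0.40:
- Habituation: 0.70 + 0.30 × 0.20 = 0.76
- Readaptation: 0.40 + 0.60 × 0.20 = 0.52
- Difference: 24 points

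| Share of failures retreated | Difference, s = 75% | Difference, s = 40% |
|---|---|---|
| 0 | 30 | 30 |
| 25% | 24.4 | 27 |
| 50% | 18.8 | 24 |
| 75% | 13.1 | 21 |

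A smaller starting difference shrinks by the same factor. With 75% against 50%, 25 points becomes 15.6 at u = 0.50 and s = 0.75 (25 × 0.625), or 20 at s = 0.40 (25 × 0.80).

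**Step 3. Unequal uptake.** The factor assumes the same uptake among failures in both groups. If failures in Group 2 seek further treatment more often, the dilution is larger. With u = 0.25 in Group 1, u = 0.50 in Group 2 and s = 0.75, the rates are 0.70 + 0.30 × 0.1875 = 0.756 and 0.625, a difference of 13.1 points.

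**Step 4. Under the second reading**, u = 0 up to the last comparison, the factor is 1 and nothing is lost.

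**The case against.** The strongest answer is that the permission is itself a safeguard. It allows further treatment only once follow-up is over, and Description of the Study Design describes the late contacts as "compared immediately after treatment and up to one year of follow-up phone calls". On that wording, follow-up lasts until the final call and no compared score comes after permitted further treatment. This is a fair reading and it makes the harm conditional. It does not remove the contradiction, because the summary stops follow-up at 6 months.

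Second, Aim 2 names its comparison times as immediate and 6 months, and the permission touches neither. This stands. A reader might infer that the trial's whole test of durability is compromised. The text does not support that: only the 6-to-12-month telephone comparison is exposed.

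Third, how scores after further treatment enter the analysis is ordinary SAP content, and the SAP is not at hand. This also stands, so the absence of a scoring rule from the protocol is not the point here. But a SAP cannot settle when the protocol's follow-up ends, nor recover dates of further treatment that nobody collected.

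Fourth, the illustration is generous at its upper end. It applies an immediate 75% success rate as if it lasted, among patients who have already failed or relapsed. The 40% column is shown for that reason. The permission also covers any participant, so selective uptake by failures is a plausible inference and not something the protocol states.

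Finally, a reader might infer that dilution follows however the one-year call is scored. It does not, since a rule that separates scores obtained after further treatment removes it. The protocol's own criterion also requires improvement in objective as well as subjective symptoms. Posturography and the rotational time constant cannot be measured by telephone, so the one-year success modelled above is not strictly the protocol's definition.

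**Conclusion.** The protocol contradicts itself on when follow-up ends, and access to further treatment is tied to that undefined point. If it is 6 months, further treatment can dilute the 6-to-12-month comparison; if it is the last one-year call, it cannot. The Aim 2 comparison at 6 months holds on both readings, provided the permission is applied as written.

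Under the 6-month reading, with an assumed 30-point difference and half of the failures in each group retreated, the late difference falls to about 19 points (retreatment success 75%) or 24 points (40%). These figures rest on assumed long-term rates, assumed uptake, lasting success after retreatment and no late relapse among responders. They show direction and order of size and are not a forecast. The documents do not support saying that crossover will erode the long-term comparison, only that the present wording allows it. The point deserves correction because durability is the aim and the repair is cheap if made beforehand.

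**What to change.** 1. Reconcile the opening summary, Specific Aim 2, Description of the Study Design and Results of the Study so that one stated time ends follow-up. The comparison of assigned treatments should not run past the point at which further treatment becomes available. When that point falls is a clinical decision for the investigators, and this review proposes none.
2. At every contact, including telephone calls, record any further habituation or readaptation, with type and date.
3. Report scores obtained after further treatment separately from the comparison of assigned treatments, or handle them under a rule fixed in advance. Counting every retreated patient as not having retained benefit is one possible rule. It would misclassify a responder who chooses more treatment, so the choice can be left to the SAP.

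The cost is a few lines of protocol wording and one more question per contact. Some late scores will leave the main comparison. Depending on how the sections are reconciled, the time at which a participant can obtain further treatment may differ from what staff now assume, and the investigators should weigh that openly.
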